391 Power Analyses: This pilot study is not powered for formal efficacy or mechanistic hypotheses testing. Consistent with 392 research regarding the purpose of a pilot study, our main interests were to evaluate the feasibility of the proposed recruitment, 393 assessment, and treatment protocols, examine safety, and to explore a detectable effect of tDCS across outcomes in 394 preparation for a larger trial (Kraemer et al., 2006; Leon et al., 2011). Although the statistical power of this study is limited, we 395 will perform statistical analyses appropriate for an adequately powered study to identify data analysis issues germane to 396 future planning.

Data Analyses: Prior to developing statistical models, all variable distributions will be examined using frequency distributions,
 scatter plots, and histograms. Statistics such as means or proportions, standard errors, ranges, and estimates of skewness
 and kurtosis will be computed and used as guidelines in the application of analyses. Data transformation procedures may be
 applied to variables with considerable departure from normality.

402

The objectives of this study are to evaluate the safety, feasibility, and PTSD symptom reductions associated with tDCS vs. sham. All statistical analyses will be intent to treat and include all participants randomized at baseline regardless of the statistical analyses will be intent to treat and include all participants randomized at baseline regardless of the

Title: Safety, feasibility, and benefits of transcranial direct current stimulation (tDCS) in human subjects with PTSD receiving an exposure-based, behavioral therapy

extent of study participation. Given the small sample size, we will use a Benjamini-Hochberg Adjustment procedure to mitigate the false discovery rate (two tailed initial p = .05). Analyses will be done SPSS 27 statistical software. As needed, we also have access to SAS 9.4, Stata 14.2, R, and Mplus 8.4 software.

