418 Generalized Linear Mixed Models (GLMM) to Address Aim 3: GLMM will be used to evaluate changes in continuous outcomes associated with tDCS vs. sham. GLMMs are a powerful and flexible statistical extension of linear mixed models 419 420 that can examine outcome variables from different distributions, such as normal (continuous) and binary outcomes. Advantages of likelihood-based regression models over conventional ANOVA include the ability to use data from all 421 participants even if they have only baseline data, relaxation of the assumption of equal variances before and after 422 423 treatment, specification of data distributions other than normal such as Poisson or log-normal, and the ability to analyze 424 longitudinal data in the presence of missing data given the assumption that data are missing at random. GLMM's will 425 include fixed effects of time, treatment (tDCS vs. sham), and the time by treatment interaction. Models will include a priori planned contrasts of mean differences over time and simple effects to evaluate treatment differences at each time point. 426 To inform future studies, we will calculate conventional effect sizes with 95% confidence interval limits (Hertzog, 2008). 427 Hedges' q will be used to calculate continuous outcome effect sizes (e.g., PCL-5). Hedges' q has been recommended 428 over Cohen's d for small samples based on sample size adjustments, yet can be interpreted using the same conventional 429 recommendations as Cohen's d, .20 =small, .50=medium, and .80=large effect sizes (Lakens, 2013). 430 431

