Assessment timepoints are presented in the 7.3 Table. The PCL-5 will be the primary outcome to evaluate changes in 432 PTSD severity from baseline assessment to one-month follow-up, with data points collected during treatment also 433 included in models (Aim 3a). Heart rate monitoring and GSR will be used to evaluate physiological stress arousal during 434 435 the writing exposure task (Aim 3b). Both physiological outcomes will be collected during the writing exposure portion of sessions 1, 3, and 5 to provide before, after, and peak estimates of physiological arousal. Time points of interest for 436 437 physiological outcomes will be the immediate, long-term, and peak effects of tDCS. The immediate effect of tDCS will be 438 defined as changes immediately prior to and after the first written exposure (i.e., change from T_1 to T_2), the third written 439 exposure (change from T_3 to T_4), and the last time participants engage in writing exposure (change from T_5 to T_6). The 440 long-term effect of tDCS will be defined as changes in physiological levels across sessions (session 1 to session 5) prior 441 to engaging in the writing exposure (change from T_1 to T_5) and after the writing exposure (change from T_2 to T_6). The *peak* effect will evaluate change score differences (interaction effect) in the greatest estimate during session 1 to session 5. 442

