Title: Safety, feasibility, and benefits of transcranial direct current stimulation (tDCS) in human subjects with PTSD receiving an exposure-based, behavioral therapy

516 **Safeguards for Protecting Participants**: Based on existing literature on tDCS, WET, and PTSD, we have developed 517 exclusionary criteria and safety protocols to mitigate, regularly screen, and respond to possible risks that may occur 518 during study participation.

519

520 tDCS: To safeguard against potential tDCS risks, we have developed exclusionary criteria related to the individual's 521 medical, psychiatric, and substance use history and known contraindications to brain stimulation (see 7.1.2 Inclusion and Exclusion Criteria). Furthermore, prior to enrollment in the study. [name] (Co-I, medical attending) and 522 [name], PsyD (PI) will review participants' assessment materials to confirm eligibility. In addition to eligibility 523 determination, we will also implement safety procedures during study participation. Participants will be monitored for AEs 524 at each treatment session and the one-month follow-up appointment. Reported AEs will be adjudicated at weekly study 525 team meetings. In these meetings additional safety monitoring of a participant may be developed. Individuals will also 526 complete the tDCS Reactions form at the end of each session to assess safety. Furthermore, the device includes 527 528 programmable features (intensity and duration) to mitigate session variation and the tDCS equipment includes 529 standardized presets for efficient and reliable electrode positioning. A study team member will also be in immediate proximity of the participant during tDCS should they require assistance or experience a serious AE. The device also has 530 an abort button that can terminate the session and ramp down the current, as needed. Lastly, we will also monitor 531 individuals for 15-30 minutes following tDCS prior to leaving the appointment. This portion of the appointment aligns with 532 the WET protocol but allows for additional time to monitor the participant for AEs. In the event it is determined the 533 534 individual requires emergency medical services, 911 will be alerted so that the individual can be taken to the nearest 535 emergency department (e.g., University Hospital). 536

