Participation in the study may be discontinued by the principal investigator if continued participation is considered a 584 585 danger to a participant's welfare. Reasons for discontinuation include: 1) a serious AE such that continued participation would be a danger to the participant; 2) clinical worsening for any reason that is deemed to necessitate non-study 586 psychological or medical treatment; 3) exacerbation of PTSD, anxiety, or depressive symptoms that the participant cannot 587 tolerate; or 4) discontinuation would be in the participant's best interest. Participants deemed candidates for 588 discontinuation will be discussed in conference calls with relevant study team members and will be brought to the 589 590 attention of the PI and Co-I's for discussion and final decision. Participants who are discontinued from the study for any 591 reason will be scheduled for a final evaluation within one week and given appropriate treatment referrals. If participants 592 are discontinued due to a serious AE, they will continue to be followed clinically by the therapist and/or member of the research staff until the AE is resolved or becomes stable. The reason the participants are discontinued from the study will 593 594 be documented for future study planning. 595

596 **11.0 TIME REQUIRED TO COMPLETE THE RESEARCH (including data analysis).**

The following table provides an overview of activities that the research team plans to accomplish. This funding mechanism is for two years. Funds will be transferred following IRB approval. Therefore, we have accounted for a 6 month "pre-award" period to submit for IRB approval, prepare study materials, and train staff in the table below, with the study time period initiating upon award transfer. We anticipate recruiting and treating 2-3 eligible participants per month to meet study goals.

601

	Pre Award	Start	Year 1			Year 2				
Study Activities (Months)	6 months		0-3	4-6	7-9	10-12	13-15	16-18	19-21	22-24
IRB Approvals, Prepare Materials, Train Staff										
Recruit, Screen, and Treat 40 Participants			Х	Х	Х	Х	Х	Х		
Follow-up Assessments				Х	Х	Х	Х	Х	Х	
Data Cleaning and Analysis							Х	Х	Х	Х

602

603 12.0 STUDY CLOSURE PROCEDURES.

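### Section 10 gives discontinued participants a last evaluation within one week and names no later research assessment, so their one-month PCL-5 and adverse-event query are likely to be missing

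*Combined protocol and SAP*

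**What the plan says.** Section 10.0 begins with discontinuation by the principal investigator on welfare grounds. One of its listed reasons is "exacerbation of PTSD, anxiety, or depressive symptoms that the participant cannot" tolerate; others are a serious adverse event and clinical worsening. It then says that a participant discontinued for any "reason will be scheduled for a final evaluation within one week and given appropriate treatment referrals". The one later contact is for those who "are discontinued due to a serious AE, they will continue to be followed clinically" until the event resolves or is stable. The section does not say what the evaluation contains, or whether outcome collection ends with it. Section 8.1 (safeguards for WET) has high-suicide-risk participants who are disenrolled referred on, again with no later assessment named.

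The table in Section 7.3 runs from baseline through sessions 1 to 5 to one post-treatment column. It has no column for a discontinuation evaluation.

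The analysis depends on the one-month data. Section 7.4.3 states: "All statistical analyses will be intent to treat and include all participants randomized at baseline regardless of the" extent of participation. The PCL-5 is to measure change in "PTSD severity from baseline assessment to one-month follow-up, with data points collected during treatment also" entering the models, which are said to handle "longitudinal data in the presence of missing data given the assumption that data are missing at random". The same section adds: "To inform future studies, we will calculate conventional effect sizes with 95% confidence interval limits". For safety, Section 8.1 has participants monitored for adverse events "at each treatment session and the one-month follow-up appointment", and Section 14.2 (item 10) gives the same schedule.

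Two general passages bear on this. Section 7.3.2.1 promises reasonable efforts to collect data and allows phone, video or electronic collection. Section 7.5 offers video at one month when travel is not feasible. Neither mentions discontinued participants.

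**The concern.** An intent-to-treat analysis keeps a discontinued participant in the model but does not supply a one-month score that nobody collected. Some of the listed reasons for stopping, namely clinical worsening and intolerable symptom exacerbation, are tied to the outcome itself; a serious adverse event need not be. The PCL-5 is taken before each session, so worsening during or after the last session attended has no scheduled PCL-5 to record it. In that case missing at random becomes harder to defend, and the arm with more discontinuations would look better than it was.

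Safety is Aim 1. The adverse-event question asks about worsening since the last visit, and the tDCS reactions form covers only the end of each session. A participant who is discontinued and not seen at one month therefore has no scheduled structured query for later events, unless the final evaluation includes one, which the protocol does not say.

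At stake are the effect sizes meant to guide a larger trial and the completeness of the safety record.

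**Working it through.** **The plan's own figures (Section 7.4.1).** 50 consented x (1 - 0.20) = 40 randomized. 40 x 0.15 = 6 lost and 40 - 6 = 34 completers. Both reproduce. The 6 pools every kind of drop-out and withdrawal, and no split is given, so the number affected by Section 10 lies between 0 and 6 (0% to 15% of 40).

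**What is still observed.** The PCL-5 is planned 7 times: baseline, five sessions and one month. Someone stopped after session 1, 2, 3 or 4 has already given 2, 3, 4 or 5 of them. These stay in the model, so missing at random can hold where the worsening already shows in them.

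**Illustration of size.** None of these inputs is in the documents; all are assumptions:
- 20 participants per arm;
- unobserved one-month scores 5 to 15 points worse than the model predicts from the observed scores;
- PCL-5 SD of 12 to 18 (the scale runs 0 to 80: 20 items scored 0 to 4).

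Formulas:
- Bias = (difference between arms in number missing) / 20 x gap.
- SE = SD x sqrt(1/n1 + 1/n2), with n1 and n2 the one-month scores observed.
- SE ratio = sqrt(1/n1 + 1/n2) / sqrt(1/20 + 1/20).

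| Missing by arm | Observed | Bias (points) | SE (points) | Bias / SE | SE ratio |
|---|---|---|---|---|---|
| 3 v 3 | 17 v 17 | 0 | 4.12 to 6.17 | 0 | 1.08 |
| 1 v 0 | 19 v 20 | 0.25 to 0.75 | 3.84 to 5.77 | 0.04 to 0.20 | 1.01 |
| 2 v 0 | 18 v 20 | 0.5 to 1.5 | 3.90 to 5.85 | 0.09 to 0.38 | 1.03 |
| 6 v 0 | 14 v 20 | 1.5 to 4.5 | 4.18 to 6.27 | 0.24 to 1.08 | 1.10 |

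Worked line for 6 v 0: bias = 6/20 x 5 = 1.5 and 6/20 x 15 = 4.5. sqrt(1/14 + 1/20) = 0.348, so SE = 12 x 0.348 = 4.18 and 18 x 0.348 = 6.27. The ratios are 1.5/6.27 = 0.24 and 4.5/4.18 = 1.08.

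In standardized units, which is how Section 7.4.3 will report effects, bias/SD is 0.25/18 = 0.01 to 0.75/12 = 0.06 at 1 v 0, and 1.5/18 = 0.08 to 4.5/12 = 0.38 at 6 v 0.

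The SE here takes no credit for baseline and session scores. Crediting them would lower the SE and raise the ratio for a given gap; the gap itself is already defined as what those scores fail to predict.

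**The case against.** The strongest reply concerns scope. Section 10 is framed around investigator discontinuation for welfare reasons. Someone who merely stops attending sessions is not clearly taken off the one-month schedule. The intent-to-treat statement, the reasonable-efforts clause and the remote options all point towards following that person. A reader might infer that all six expected losses would lack one-month data because of Section 10. The documents do not support that: the phrase covering any reason is broad, but the six are a pooled figure and the share discontinued under Section 10 could be none. This part of the reply stands.

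A second reply is that the evaluation within a week may be a prompt safety step, and that Section 10 never says the one-month visit is cancelled. That also stands as far as it goes. The word used for the evaluation implies that nothing follows, but it does not settle the matter, and the unseen figure or procedures could.

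Third, much is already covered. Session PCL-5 scores stay in a likelihood-based model, Aim 3 is exploratory, the pilot is not powered for efficacy, and serious adverse events that lead to discontinuation are followed clinically. So two further inferences, that missing at random must fail or that safety data on these people are lost altogether, also go beyond the text.

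What survives is narrower. The general clauses promise to collect the data that the protocol describes, and for discontinued participants it describes one evaluation of undefined content and no one-month visit.

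**Conclusion.** The gap is real on the visible text, and it is modest. Section 10 does not separate stopping treatment from ending data collection, and no visible passage keeps discontinued participants on the one-month schedule that the PCL-5 analysis and the last adverse-event query rely on. That their data are likely to be missing is an inference, held with medium confidence.

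The number affected is 0 to 6 of 40. The expected effect is small: nil with an equal split and at most 0.20 SE at 1 v 0. Only the unlikely 6 v 0 split with the largest assumed gap and smallest assumed SD reaches about one SE, with the SE itself up by about 10%. Every bias figure rests on the assumed arm sizes, gap and SD.

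This does not threaten the pilot's main purpose. It is still worth correcting, because scores and adverse events that are never collected cannot be recovered in the analysis.

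**What to change.** In Section 10:
- Separate stopping study treatment from ending data collection.
- State that, unless consent is withdrawn, discontinued participants are still asked for the PCL-5, the adverse-event query and the Health Questionnaire when their one-month follow-up would have fallen, remotely if needed. Sections 7.3.2.1 and 7.5 already allow remote follow-up.
- Define how that date is set for someone who stops early; the documents do not say.
- State what the evaluation within one week contains. If it includes a PCL-5, give the recall window, since Section 14.2 uses one week during treatment and two weeks otherwise.

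In Section 7.4.3, state that any such PCL-5 enters the model at its actual time and is not used as the one-month value.

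Cost: a few protocol sentences, one analysis sentence and at most about six extra remote contacts. The downside is contacting people who have stopped treatment, whose one-month scores may partly reflect non-study care. The Health Questionnaire already asks about services and medications, so that care can be described. No clinical stopping rule changes.

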7.3.2 Data Collection. See Table in Section 7.3 for a summary of the assessments and timing of administration. The data collected in the study will be coded using an assigned number. Hard copies of data collected during the study will be securely stored in locked cabinets at the STRONG STAR offices. Data will be entered into the STRONG STAR database by a member of the research team.

7.3.2.1 Instrumentation. See the table in Section 7.3 for a summary of the assessments and timing of administration. A
 description of each of the assessments can be found at the end of this protocol. Assessments will be administered in
 person whenever possible. However, to accommodate participant schedules and/or instances in which a participant does
 not reside in the local area at the time of a follow-up assessment, we may collect full or partial assessments in person or
 yia phone, video conferencing, and/or electronic data capture using a secure link to the encrypted STRONG STAR
 database. Reasonable efforts will be made to collect all data as described in this protocol, but we expect some

344 participants may not be able to complete part or all of any given follow up assessment.

Title: Safety, feasibility, and benefits of transcranial direct current stimulation (tDCS) in human subjects with PTSD receiving an exposure-based, behavioral therapy

Study Day	Pre/BL	S1	S2	S 3	S4	S5	Post
Informed Consent	R						
Interventions							
tDCS/Sham		R	R	R	R	R	
WET		R	R	R	R	R	
Clinical Interviews	·			•		•	
1. Clinician Administer PTSD Scale-5 (CAPS-5)	S,R						R
2. STRONG STAR Health Questionnaire	S,R						R
3. Health Questionnaire Addendum for tDCS	S,R						
 Self-Injurious Thoughts and Behaviors Interview (SITBI) 	S,R						R
Self-Report Questionnaires		-					
5. PTSD Checklist-5 (PCL-5)	R	R	R	R	R	R	R
6. Patient Health Questionnaire-9 (PHQ)	S,R	R	R	R	R	R	R
7. Generalize Anxiety Disorder-7 (GAD)	R	R	R	R	R	R	R
8. Posttraumatic Cognitions Inventory (PTCI)	R	R	R	R	R	R	R
 Depressive Symptom Index-Suicidality Subscale (DSI-SS) 	S,R	R	R	R	R	R	R
10. Adverse Events Monitoring		R	R	R	R	R	R
11. tDCS Reaction Monitoring		R	R	R	R	R	
12. Demographics Questionnaire	S,R						
13. Life Event Checklist-5 (LEC)	R						R
14. Brief Inventory of Psychosocial Functioning (B-IPF)	R						R
15. Quick Drinking Screen (QDS)	R						R
16. Drug Abuse Screening Test (DAST)	S						
17. Insomnia Severity Index (ISI)	R						R
 Cognitive Emotions Regulation Questionnaire (CERQ) 	R						R

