485 486 tDCS: The most common adverse effect of tDCS include mild itching sensation at the point of contact with the electrodes. These AEs can be mitigated by excluding individuals with a history of skin condition, the use of saline solution, and 487 limiting the intervention to 40 min or less with ~1-week in-between sessions. 488 489

WET: Temporary increases in psychological distress can occur among individuals engaged in WET for PTSD. 490

492 Less Likely, some may be Serious (expected to occur in 10-18 out of 100 participants):

493 494 tDCS: Transient minor discomfort can occur in about 10-18% of participants, such as mild headaches, nausea, mild 495 burning sensation at the point of electrode contact, and fatigue. However, the relatedness of AEs to tDCS remains unclear 496 as many controlled trials have demonstrated no difference between the tDCS and sham conditions.

- 498 Rare and Serious (expected to occur in <1 out of 100 participants):
- 499 tDCS: A rare but serious AE of tDCS can be skin lesions following repeated tDCS. As noted above, the risk of both skin 500 lesions and itching/burning sensations can be minimized by soaking the connecting sponges in sodium chloride (saline) 501 solution rather than water before commencement of stimulation. Another potentially serious AE that has been discussed 502 503 in the literature is seizures. To date, there is no documented evidence that tDCS has resulted in a seizure and this may be explained by the subthreshold current used in tDCS. However, there is a theoretical rationale that brain stimulation can 504 505 increase the risk of seizures.
- 506 507 Risks to Confidentiality: With the handling of medical and research records there is always the possibility of a breach of 508 confidentiality. We will maintain patients' names, contact information (i.e., Identifiers), and all PHI (protected health information) in an encrypted computer database and all PHI identifiers will be removed in the database during data 509 510 analysis. Every member of the Research Team is carefully trained and monitored about how to store, handle, and protect 511 participant records.
- 513 Risks of PTSD Diagnosis regardless of Treatment: One of the risks of PTSD both in and out of treatment is attempted 514 suicide, which can result in death. Increased suicidality is possible during study participation. 515
 - 56GTSPH3C08UU94FUFQ8ULIG00.docx STRONG STAR Template Version 01/31/22

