537 The risk for the mild itching sensation at the point of contact with the electrodes will be mitigated by excluding individuals 538 with a history of skin condition, the use of saline solution, and limiting the intervention length to 30 min with ~1-week in-539 between sessions.

540

541 WET: Psychological distress experienced by participants is expected to be temporary and participants will be provided immediate coping tools and techniques to manage distressing emotions by the study therapist. Any indication that the 542 participant is considering suicide, endorses active psychosis/mania, or other harm to self/others will be handled using 543 evidence-based procedures and policies developed by the STRONG STAR Consortium. Participants who endorse 544 mania/psychotic symptoms will prompt a clinical interview with a licensed clinical provider to assess current risk and risk 545 of active mania/psychosis during study participation. Individuals with active mania/psychosis will be excluded from study 546 547 participation. Trained clinicians and evaluators will assess history of suicide and current suicidal ideation using the 548 Suicidal Ideation Thoughts and Behaviors Interview at the baseline assessment. Prior to each session individuals will also 549 complete self-report questionnaires to monitor PTSD, depression, and suicidality symptoms. Participants identified as low to moderate risk for suicide based on the assessment results may be maintained on the protocol and additional risk 550 management procedures will be implemented within the context of the study treatment. For participants identified as being 551 at high risk for suicide based on the assessment results, disenrollment will be considered if it is unlikely that standard 552 553 treatment plus additional risk management procedures will maintain safety. High risk participants who are disenrolled from 554 the study will be referred for more intensive treatment (outpatient or inpatient).

For urgent issues that occur in between appointments, whether related to tDCS or WET, participants will be instructed to get help immediately by going to the nearest emergency room. All participants will be given a study device emergency department wallet card at the beginning of the study. Participants will be instructed to keep this card on their person throughout the study. The wallet card briefly describes the study intervention (tDCS vs. sham) and provides a study team contact number.

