- 643 Health Questionnaire tDCS Addendum. The Health Questionnaire tDCS Addendum is an adapted extension of the Health 644 3. Questionnaire and includes items relevant to the assessment of tDCS health contraindications. Items will assess for 645 history of seizures, significant intracranial pathology (e.g., severe traumatic brain injury), major neurological conditions 646 (e.g., Dementia), metallic objects in the body, skin conditions where electrodes are applied that could be exacerbated 647 (e.g., eczema), and adverse reaction to brain stimulation. This measure will be administered at the baseline assessment. 648
- Self-Injurious Thoughts and Behaviors Interview (SITBI). The SITBI (Nock et al., 2007) is a structured interview assessing 650 4. the presence, frequency, and characteristics of self-injurious and suicidal thoughts and behaviors. The SITBI will be 651 administered by an Independent Evaluator, who will instruct the participants to answer the questions based on their entire 652 653 lifetime of experience. The SITBI has shown high interrater reliability, test-retest reliability, and concurrent validity. This 654 measure will be administered at the baseline assessment and the one-month follow-up assessment.

14.2 Self-Report Questionnaires:

649

655

- 656 PTSD CheckList-5 (PCL-5). The PCL-5 (Weathers, Litz, et al., 2013) is a 20-item self-report measure update of the PCL 657 5. designed to assess PSTSD symptoms as defined by the DSM-5. The PCL-5 is currently available and has been shown to 658 have good psychometric properties. The PCL-5 evaluates how much participants have been bothered by PTSD 659 symptoms in the past week (for all assessments during treatment) or the past two weeks (all other assessment time 660 points) as a result of a specific life event. Each item of the PCL-5 is scored on a five-point scale ranging from 0 "not at all") 661 to 4 ("extremely). This measure will be administered at the baseline assessment, prior to each therapy session, and the 662 one-month follow-up assessment. 663

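### Lifetime recall for the SITBI at both baseline and one month shows on-study self-injury only indirectly, and does not match its baseline use for current suicidal ideation

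*Combined protocol and SAP*

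**What the plan says.** Section 14.1, item 4, describes the SITBI as a structured interview covering "the presence, frequency, and characteristics of self-injurious and suicidal thoughts and behaviors". It is given by an independent evaluator, "who will instruct the participants to answer the questions based on their entire" lifetime. On timing, the same item says that the "measure will be administered at the baseline assessment and the one-month follow-up assessment". The assessment table in Section 7.3 agrees: screening and research use at baseline, research use at the post-treatment visit, and nothing at sessions 1 to 5. No different recall period is given for the second administration.

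Section 8.1, under the safeguards for WET, gives the interview a purpose: "Trained clinicians and evaluators will assess history of suicide and current suicidal ideation using the" "Suicidal Ideation Thoughts and Behaviors Interview at the baseline assessment". The name differs slightly from the one in Section 14.1. The table lists only one interview of this kind, so I read both as the SITBI.

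Section 8.1 also names the risk: "Increased suicidality is possible during study participation". Section 7.4.2 assigns Aim 1 (safety) to adverse-event monitoring, and the SITBI is not a named endpoint.

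**The concern.** A lifetime question suits history-taking at entry. Asked again about a month after treatment, it mixes what happened before the trial with what happened during it. The protocol expects that suicidality may rise during participation and makes safety its first aim. The SITBI is the only structured interview described as covering self-injurious behaviour, and its follow-up form has no reference period that places an event inside the trial. Section 14.1 gives no purpose for the repeat, and Section 7.4.3 plans no comparison of the two administrations.

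The baseline use raises a separate question. If the interview is meant to establish current ideation, as Section 8.1 says, then an instruction to answer over the whole lifetime does not produce that information by itself. The SITBI is marked for screening at baseline, and exclusion criterion 8 concerns suicidality that needs immediate intervention, so the distinction between current and past matters at that visit.

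**Working it through.** There is no stated figure to reproduce. The check is a reading of recall periods, with one small calculation on the DSI-SS.

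**1. What a repeated lifetime answer can reveal.** Take one SITBI domain, such as attempts. Let B be the lifetime presence answer at baseline, N whether an event occurred on study, and F the lifetime presence answer at one month. With accurate recall, F is positive if B or N is positive.
- B negative: F equals N, so new onset is visible.
- B positive: F is positive whether or not N occurred, so the presence answer carries no information about the trial period.

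The interview also records frequency. With accurate recall, the on-study count is the lifetime count at one month minus the lifetime count at baseline. Each term is a recalled total over many years, and the difference carries the recall error of both. It may point to a new event, but only indirectly.

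This applies domain by domain. A participant with past ideation but no past attempt can still show a new attempt.

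**2. What the other measures cover.**
- *DSI-SS* (Section 14.2, item 9): the past two weeks, at baseline, before each session and at one month. As described, it covers suicidal thoughts, planning, sense of control over the thoughts, and impulses. Self-injurious acts and attempts are not in the description.
- *Adverse-event question* (Section 14.2, item 10): an open question about worsening since the previous visit, before each session and at one month. Start and stop dates, severity, functional impact and relatedness are recorded. It can capture an act of self-injury that the participant volunteers, but it is not described as asking about one.

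**3. Gaps in the DSI-SS window.** Sessions are weekly (7 days) and the window is 14 days, so ideation between session 1 and session 5 is covered without a gap. The anchor for the one-month visit is not stated. If it falls 28 to 31 days after session 5 (an assumption), the uncovered stretch is 28 − 14 = 14 days to 31 − 14 = 17 days. In that stretch only the open adverse-event question and the lifetime SITBI apply, even for ideation.

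**4. Recall periods elsewhere in the plan.** The PCL-5 window changes by time point (Section 14.2, item 5: one week during treatment, two weeks otherwise). The head-injury history form is given at baseline only. So the plan already adapts recall to the visit for one instrument and restricts a history form to entry for another.

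**5. Section 8.1 beside Section 14.1.** Section 8.1 wants both history and current ideation from the baseline interview. The instruction in Section 14.1 yields a lifetime answer, in which past and current ideation are not separated.

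**The case against.** A reader might infer that the follow-up SITBI cannot show new self-injury or suicidality at all, and that the arms therefore cannot be compared on new events. The documents do not support that. A domain that was negative at baseline can turn positive, and frequency and characteristics are recorded besides presence. A self-injury or attempt reported as an adverse event is dated and adjudicated, and can be counted by arm. Current ideation is tracked by the DSI-SS at every session and at one month. Aim 1 was never assigned to the SITBI. All of this stands, and it limits the point to weak structured capture of behaviour in participants with a prior history.

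The SITBI form is not reproduced, so its items on characteristics may record recency or dates. If they do, much of the follow-up problem disappears in practice. Section 14.1 does not say so, and the instruction it gives points the other way.

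On the baseline mismatch, a lifetime frame includes the present, and the DSI-SS is also marked for screening at baseline. No eligibility decision is shown to rest on the SITBI alone. The mismatch is therefore narrow, concerns baseline only, and may be loose drafting. It still leaves two sections describing the same interview with different time frames.

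A reader might also want a number of participants for whom the follow-up interview is uninformative. The documents give no lifetime prevalence for any SITBI domain, and one prevalence would treat a multi-domain interview as a single yes/no item. No such count can be supported.

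**Conclusion.** The point holds in limited form. At one month the SITBI, as described, shows on-study self-injurious thoughts or behaviours only indirectly. New onset is visible where the domain was negative at baseline. Where it was positive, presence is uninformative and a new event must be inferred from two recalled totals. The DSI-SS and the adverse-event question cover ideation and volunteered events, but neither is described as asking specifically about self-injury or attempts. Separately, Sections 8.1 and 14.1 must be reconciled on whether the baseline interview establishes current ideation.

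This rests on reading Section 14.1 as applying the lifetime instruction at both visits, and on the follow-up form having no dating items that the protocol leaves unmentioned. No endpoint, sample size or error rate is affected. It is a modest weakness in safety capture, worth correcting because data collected under the wrong reference period cannot be reliably repaired afterwards, and because the pilot is meant to inform a larger trial.

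**What to change.** - Section 14.1, item 4: keep the lifetime frame at baseline, and state that at one month the reference period is *since your baseline assessment*.
- Reconcile Sections 8.1 and 14.1, stating how the baseline interview records current ideation separately from history, or which instrument does so.
- Section 7.4.3: tabulate SITBI-reported new self-injurious thoughts and behaviours by arm, descriptively, beside the Aim 1 adverse-event results.
- Record the date of each new report. Section 7.1.5 allows baseline assessments up to 30 days old to be reused from another study, so the period since baseline can begin before randomization.

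The cost is a changed instruction, a date field if the form lacks one, and one more table row, with no new instrument or visit. The downside is that the follow-up wording will differ from baseline, so lifetime scores are not repeated. The plan assigns no analysis to repeated lifetime scores.
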